2.3.2 KNOWN POTENTIAL BENEFITS

This is a mechanistic study to determine the role of ovarian hormone changes in constructs that are relevant to suicidality. There is no direct benefit to the participants other than the benefit of knowing that they are contributing to research on the causes of suicidality.

3 OBJECTIVES AND PURPOSE

The purpose of this mechanistic study is to experimentally test a pathophysiologic mediational model in which late luteal (perimenstrual) ovarian steroid withdrawal increases suicidal desire (via increased hopelessness and negative social appraisals) and suicidal action capacity (via reduced inhibitory control and increased threat sensitivity). We predict that natural P4 withdrawal (compared to the two conditions in which P4 is stabilized) will increase reports of suicidal desire (partially mediated by task performance indicating increased hopelessness and negative social appraisals) and action capacity (partially mediated by task performance indicating increased hopelessness and negative social appraisals) and action capacity (partially mediated by task performance indicating decreased inhibitory control and increased threat sensitivity). Therefore, we predict that administration of P4 will reduce suicide risk by buffering the deleterious impact of perimenstrual withdrawal from P4. We predict that administration of E2 will have some mild protective effects, but not to the same extent as P4.

4 STUDY DESIGN AND ENDPOINTS

4.1 DESCRIPTION OF THE STUDY DESIGN

This is a single-center study; there is no phase designation because it is a mechanistic experiment with agents (E2,P4) that is commonly used in clinical practice.

Participants: 60 female outpatients (recruited to achieve a targed N of 40 completers) with a with past-month suicidal ideation but **low**^{17,18} **imminent suicide risk** (see **Human Subjects**) receiving treatment as usual. Participants must: be 18 to 45 years of age, have normal menstrual cycles (21-35 days), not pregnant, breastfeeding, or trying to get pregnant, not taking hormones, no history of serious medical illness, normal weight (BMI 18-29.99), and low risk for thrombotic events (factor V Leiden mutation based on family history). *Most outpatients with suicidality take medications; therefore, to increase feasibility/generalizability, medication use will be measured and covaried in analyses (as in the similar study recently completed by the PI).*

Psychiatric Diagnoses. The SCID-I and SCID-II. *History of manic episode, psychosis, or substance abuse disorder will be exclusionary due to risk of suicidal crises*^{17,100}. Additionally, self-report history of postpartum depression or premenstrual dysphoric disorder are exclusionary, since reproductive mood disorders may be characterized by a different pattern of sensitivity¹⁰¹. Based on data from the preceding study, we expect 90% of our sample to have lifetime depressive disorder, 50% to meet criteria for BPD, and 50% to have lifetime anxiety disorder.

Study Design (Fig 2). THIS IS NOT A CLINICAL EFFICACY

(Condition B) or P4 (Condition C) will be maintained for 14 days by applying a new patch on day +14 (extended luteal phase levels spanning +7 to +21), preventing natural withdrawal and stabilizing E2 or P4 in physiologic¹⁰² luteal range. In the prior study, this dosing schedule resulted in a stabilized, slower hormone taper as both endogenous hormones were naturally falling during the perimenstrual experimental time period, with exogenous hormone slowing/buffering this decline during the active phase. Of note, the placebo condition uses the same patch/pill schedule.

Assessment of Outcomes. In addition to daily surveys, participants will complete phone measures starting at ovulation and ending 5 days following the last patch/pill. Three lab sessions will assess serum E2, P4, and ALLO, and behavioral outcomes.

Lab Construct Measures. Each computerized task is scored using within-task comparisons, controlling for training-related changes in response time. **Hopelessness** will be measured via the Future Thinking Implicit Relational Assessment Procedure (FT-IRAP)¹⁰³; participants respond with *true* or *false* to pairings between "I expect" and "I don't expect" with sets of negative (e.g., worry, sadness) and positive (e.g., enjoyment, happiness) events. Greater latency to optimistic/hopeful, and lower latency to pessimistic/hopeless pairings indicate implicit hopelessness¹⁰³. Performance predicts clinical hopelessness and depression¹⁰³. Negative **Social Appraisals** will be measured using the Social Acceptance-Rejection Implicit Association Test (SAR-IAT)¹⁰⁴, in which participants respond to pairings of *self* words (e.g., I, me) and *other* words (e.g., them, you) with words indicate the strength of implicit self-with-acceptance or self-with-rejection associations. Performance predicts explicit social

appraisals and negative affect in social interactions¹⁰⁴. *Inhibitory Control* will be measured using the Stop-Signal Task (SST)¹⁰⁵; participants withhold a prepotent response. Performance predicts prefrontal cortex activation and lower impulsive clinical outcomes¹⁰⁵. *Threat Sensitivity* will be measured as attentional bias for threat pictures on a Dot Probe Task (DPT)¹⁰⁶. Attentional bias to threat on this task is linked to anxiety disorders¹⁰⁷ and multimodal indices of threat sensitivity in daily life^{106,108}. *Parasympathetic* influences on the heart will be quantified using electrocardiogram, which will be collected and cleaned according to established evidence-based protocols. *Respiratory Sinus Arrhythmia (RSA)* will measure of parasympathetic (vagal) influence, and will be calculated using the well-validated peak-valley method. Greater RSA values reflect greater parasympathetic activity. RSA will be evaluated for a 10-minute baseline. *Concurrent Suicidal Desire* and *Action Capacity* will be estimated with the Suicidal Ideation, Thoughts, and Behavior Interview (SITBI)¹¹². *Validity* will also be examined with a wide variety of well-validated self report laboratory measures of the above constructs; all items of these measures are provided in the appendix.

Daily Online Symptom Measures: A variety of items intended to capture a wide array of symptoms related to the above constructs; all items are provided in the appendix.

Daily Safety and Suicidality Telephone Call: Suicidal desire and action capacity will be measured with a daily telephone call during active condition days using a shortened version of the SITBI¹¹². Items are provided in the appendix.

Participant Safety: As in the preceding experiment, emergent changes in suicidality will be managed using the structured University of Washington Risk Assessment and Management Protocol (UWRAP)^{24,116}. However, because the manipulation mimics luteal E2/P4 levels that females **naturally** experience, the manipulation is not expected to pose greater risk than a normal¹⁰² cycle—the risk will simply be shifted during P4 stabilization. This is supported by the results of the prior experiment.

Primary Windows of Comparison for Hypothesis Testing. To test whether prevention of P4 withdrawal (in Condition C) reduces the perimenstrual increase in suicide risk, **primary** hypothesis tests will compare degree of suicide risk (as measured with self-report, tasks, and interviews) during the perimenstrual weeks of each condition (days +7 to +22). **Secondary** analyses will examine Condition C, testing whether tapered withdrawal from exogenous P4 around days +16 to +22 causes "shifted"/"postponed" perimenstrual risk.

Hypotheses/Analytic Plan. It is hypothesized that Condition A (E2/P4 withdrawal under placebo) and Condition B (P4 withdrawal under E2 stabilization) will BOTH be associated with heightened perimenstrual suicidality, but that Condition C (E2 withdrawal under P4 stabilization) will significantly reduce perimenstrual increases in suicidality. We also hypothesize that a steeper slope of ALLO withdrawal, calculated across the lab ALLO measures in each condition, will mediate the more deleterious effects of P4 withdrawal conditions. Multilevel models will be used (repeated observations nested within individuals) to predict daily or weekly repeated suicidality and mediator outcomes from a within-person condition factor (and, if appropriate, the interaction of condition and day). Mediation by degree of ALLO withdrawal will be tested by estimating a 95% CI for the indirect effect of condition (focal predictor) on suicide risk outcomes (dependent variable) via the slope of ALLO change across the perimenstrual phase (mediator). **Power Analysis**. For primary hypothesis tests, 80% power to detect a conventionally medium-sized effect of condition (f = .25) is achieved with 24 participants¹¹⁷. To allow for attrition and improve generalizability and power, we propose to include 30 participants.

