6.1.9 DURATION OF THERAPY

The planned duration of active treatment is 14 days. All days in which participants use patches and pills will be utilized in multilevel modeling analyses, which accommodate unbalanced/missing data.

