10.2 STATISTICAL HYPOTHESES

Hypotheses. For suicidal desire and suicidal action capacity—our primary endpoints)—we predict that perimenstrual increases in suicidal desire and action capacity (Lab 2 – Lab 1 within each condition) will be larger in the placebo (natural E2 + P4 withdrawal) condition and experimental E2 stabilization (P4 withdrawal) condition than in the experimental P4 stabilization (E2 withdrawal) condition. The associated null hypothesis is that there will be no difference in the perimenstrual increase in suicidality across conditions. For our secondary endpoints, including hopelessness, negative social appraisals, reduced inhibitory control, and threat sensitivity, we predict the same pattern of results.

There are no "efficacy" endpoints in the present trial since it is mechanistic and not a treatment study.

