10.4 DESCRIPTION OF STATISTICAL METHODS

10.4.1 GENERAL APPROACH

The design of this study is a three-period crossover design, where each of three study periods is a perimenstrual frame of the menstrual cycle (days +7 to +22 following ovulation where positive ovulation test day=0). Each participant will complete all three conditions in a randomized order.

Primary hypothesis tests will be evaluated using a alpha level of .05, with a two-tailed test.

All outcomes will be checked for normality; given the low likelihood that suicidality will follow a normal distribution even in this clinical sample, we expect that we will need to utilize nonparametric procedures.

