10.5 SAMPLE SIZE

An unlimited number of potential participants will be screened. 60 females will be enrolled in the study, with the goal of 40 participants completing the study.

Power analyses are described below; alpha is set at .05, power at 80%. The null hypothesis is no link between the study experimental condition and risk for suicidal ideation, intent, and planning; the alternate hypothesis is that hormone stabilization in the experimental condition will prevent flux in these suicide-related outcomes. Because no previous studies have examined the impact of experimental hormones on suicidality, we have conducted power analyses using existing effect sizes on related constructs (e.g., BPD features).

Power Analysis. For primary hypothesis tests, 80% power to detect a conventionally mediumsized effect of condition (f = .25) is achieved with 24 participants¹¹⁷. To allow for attrition and improve generalizability and power, we propose to include 40 participants in the final sample.

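### The daily or weekly multilevel model names only the woman as a nesting level; if fitted with a woman intercept alone, its condition test can exceed the stated .05, and nothing says whether this model or the condition-mean ANCOVA governs

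*Combined protocol and SAP*

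**What the plan says.** Section 4.1 (Hypotheses/Analytic Plan): "Multilevel models will be used (repeated observations nested within individuals) to predict daily or weekly repeated suicidality and mediator outcomes from a within-person condition factor", with a condition-by-day interaction where appropriate. Section 6.1.9 adds: "All days in which participants use patches and pills will be utilized in multilevel modeling analyses, which accommodate unbalanced/missing data". Neither section states the random effects or a residual correlation structure.

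Section 10.4.1 describes a three-period crossover: "Each participant will complete all three conditions in a randomized order". It also sets the error rate: "Primary hypothesis tests will be evaluated using a alpha level of .05, with a two-tailed test". Section 10.2 gives the null: "The associated null hypothesis is that there will be no difference in the perimenstrual increase in suicidality across conditions".

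Section 10.4.2 plans a different analysis for the two primary and five secondary endpoints. Daily phone ratings are averaged to one value per woman per condition, and those values go into a repeated measures ANCOVA, or a nonparametric counterpart if assumptions fail. Section 10.1 says that no formal SAP will be written. No section ranks the two analyses.

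**The concern.** A condition is assigned to a woman's cycle, and there are three such units per woman. Every day in a cycle shares the condition, and also shares whatever else made that month better or worse. With only a woman-level intercept, the model treats about 14 days as separate pieces of evidence on the condition, given the woman's overall level. Ordinary differences between a woman's cycles, or ideation that persists from one day to the next, then enter the condition contrast without entering its standard error in full.

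Such variation is plausible here. Participation lasts six to seven months on treatment as usual, and recent extreme stressors are screened only at entry. At stake is whether a finding that hormone withdrawal raises suicidality keeps its nominal error rate.

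**Working it through.** **The plan's own figure.** Section 4.1 states that "80% power to detect a conventionally medium-sized effect of condition (f = .25) is achieved with 24 participants". For a repeated-measures F test with noncentrality f²·n·k/(1−r), three conditions and r = .5 need 28 women (power at 24 is .741). The required number is 25 at r = .55 and 23 at r = .60, and k = 4 with r = .5 gives 24. Neither r nor k is stated, so 24 cannot be called wrong. It does not affect what follows.

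**Inputs from the documents.** Three conditions, one cycle each (4.1, 10.4.1). n = 40, since section 10.5 says "we propose to include 40 participants in the final sample" (section 4.1 says 30; at n = 24 the re-computed rates differ by at most .002). m = 14 treated days (6.1.9), 7 days (endpoint definition, 4.2.1) or 3 lab visits (4.1). Two-sided alpha .05.

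**Assumed.** ρ, the share of within-woman variance lying between cycles, and any day-to-day correlation. The documents give neither.

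**Formula.** Scale within-woman variance to 1. With no condition effect:

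- The condition mean square has expectation v = (1−ρ) + mρ on 2 df.
- The intercept-only model pools the woman-by-cycle stratum (2(n−1) = 78 df, expectation v) with the daily residual (3n(m−1) df, expectation 1−ρ). Call the pooled expectation p.
- The omnibus rejection rate is approximately exp(−F.95·p/v). For A versus C it is approximately P(|Z| > 1.96·√(p/v)).

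**Worked case, m = 14, ρ = .10.** v = .90 + 1.40 = 2.30. p = (78×2.30 + 1560×.90)/1638 = .967. F.95 = 3.001. Omnibus: exp(−3.001×.967/2.30) = .283.

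| m | ρ | v | p | Omnibus | A vs C |
|---|---|---|---|---|---|
| 14 | 0 | 1.00 | 1.000 | .050 | .050 |
| 14 | .05 | 1.65 | .983 | .167 | .130 |
| 14 | .10 | 2.30 | .967 | .283 | .204 |
| 14 | .20 | 3.60 | .933 | .459 | .318 |
| 7 | .10 | 1.60 | .968 | .162 | .127 |
| 3 | .20 | 1.40 | .947 | .129 | .106 |

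Simulations of the three inflated 14-day settings give omnibus rates of about 16–18%, 27–29% and 45–47%. Those of the 7-day setting give 15–17%, and of the weekly setting 13–14%.

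**Serial correlation alone.** With AR(1) = 0.3, ρ = 0 and m = 14, the variance of a cycle mean is multiplied by 1.770, so v = 1.770 and p = .980. The omnibus rate is exp(−3.001×.980/1.770) = .190; simulations give 18% to 19.5%.

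**Condition by day.** A shift of a whole cycle cancels out of within-cycle slopes but still enlarges p. The rate is exp(−3.001·p/(1−ρ)) = .045, .040 and .030 at ρ = .05, .10 and .20, which is slightly conservative. With AR(1) = 0.3 and ρ = 0, the slope variance is multiplied by 1.598 and the rate is .159 (simulated, about 12% to 17%).

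**Condition means.** Under this model the numerator and denominator of the section 10.4.2 test both have expectation v, on 2 and 78 df. The ratio is a true F and the rate is .050 at any ρ (calculated .04998).

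**Fitted mixed models** (n = 40, 14 days, ρ = .10). A versus C rejected 23% with a woman intercept only and 7% with a cycle-level random effect added (150 runs).

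**The case against.** The strongest reply is that the plan never commits to an intercept-only model. The wording of section 4.1 also fits a random condition slope within woman, which would absorb most of the cycle-to-cycle variation. In a small check (80 runs, so imprecise) A versus C rejected 22.5% with the intercept only and 8.75% with random condition slopes. This stands: the text is under-specified, and a reader who infers that the plan has chosen to ignore the shared cycle goes beyond it.

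Second, section 10.4.2 already protects every listed primary and secondary endpoint, and the .05 level is set in the same section 10.4. This stands if section 10.4.2 governs. But section 4.1 places the multilevel plan beside its primary windows of comparison and its power statement for primary tests, and no section settles the order.

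Third, section 10.2 frames the hypothesis as change from Lab 1 to Lab 2 within a condition. Tested as condition by time on those two visits with a woman intercept, simulated rejection was 5.0%, 3.8% and 3.0% at ρ = .05, .10 and .20. So the inflation from cycle-level shifts belongs to the condition main effect and not to that change contrast.

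Fourth, a reader might infer that the ALLO mediation interval is too narrow in the same way. That was not computed, and section 4.1 does not say how the interval is obtained. The mediation model needs a stated error structure, but no size can be attached.

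**Conclusion.** The concern holds in a limited form. If the daily or weekly model is fitted with a woman-level intercept only, its condition main-effect test can exceed .05: about 17% to 46% (omnibus) and 13% to 32% (A versus C) for 14 independent days and ρ from .05 to .20. The omnibus rate is about 16% with 7 days at ρ = .10, about 13% with three weekly values at ρ = .20, and about 19% from AR(1) = 0.3 alone with 14 days. All of these rest on assumed variance components, and with ρ = 0 and independent days the inflation vanishes.

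A reader might infer a fixed 2-to-10-fold error rate for the trial, or that condition-by-day tests suffer equally. The documents support neither. The multiple depends on ρ, on the number of days and on the contrast, and condition-by-day tests are inflated only by serial correlation or by slopes that vary between cycles. The condition-mean analysis of section 10.4.2 is sound on this point. What is missing is a statement that it governs, and an error structure for the model used elsewhere.

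**What to change.** In sections 4.1, 6.1.9 and 10.4.2, state that condition tests on the primary and secondary endpoints rest on the one-mean-per-condition analysis.

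Wherever the daily or weekly multilevel model is used for inference (trajectories, lab tasks, ALLO mediation), specify:

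- a woman-by-condition random effect in addition to the woman effect (with one cycle per condition, this is the cycle effect);
- an AR(1) residual within cycle for daily data;
- a day slope that varies by cycle where day is in the model;
- Kenward-Roger or Satterthwaite degrees of freedom.

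The cost is a few sentences and a slightly more complex model, with no extra data. Intervals will be wider than from the intercept-only model, and correctly calibrated.

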4.2.1 PRIMARY ENDPOINT

The primary endpoints (described below) of this mechanistic study are suicidal ideation and planning score differences between placebo condition and stabilization conditions on the SITBI measure. These were chosen given their strong predictive validity in epidemiological studies.

(1) Mean Within-Person Condition Differences (7 final placebo days – 7 final stabilization days) of SITB Suicidal Ideation subscale score

CLEAR 2 Study Protocol: Hormones and Suicide Risk, Version 9, 07-02-2020, Page 14 of 64

(2) Mean Within-Person Condition Differences (7 final placebo days – 7 final stabilization days) of SITB Suicidal Planning subscale score

4.2.2 SECONDARY ENDPOINTS

The secondary endpoints of this study include the daily telephone measures as follows:

- (6) Mean Within-Person Condition Differences (7 final placebo days 7 final stabilization days) of BHI Hopelessness Score
- (7) Mean Within-Person Condition Differences (7 final placebo days 7 final stabilization days) of CES-D Depression Total Score
- (8) Mean Within-Person Condition Differences (7 final placebo days 7 final stabilization days) of UPPS-P Lack of Premeditation Impulsivity subscale
- (9) Mean Within-Person Condition Differences (7 final placebo days 7 final stabilization days) of PROMIS Anxiety Total Score
- (10) Mean Within-Person Condition Differences (7 final placebo days 7 final stabilization days) of SSES Social Evaluation/ Rejection Sensitivity subscale

4.2.3 EXPLORATORY ENDPOINTS

None.

5 STUDY ENROLLMENT AND WITHDRAWAL

5.1 PARTICIPANT INCLUSION CRITERIA

In order to be eligible to participate in this study, an individual must meet all of the following general criteria:

- Provision of signed and dated informed consent form
- Stated willingness to comply with all study procedures and availability for the duration of the study
- Ability to take oral medication and be willing to adhere to the medication regimen

To be eligible for participation in the proposed study, an individual must meet all of the following criteria.

- 1. Must be biologically female and between the ages of 18-45 years.
 - **Justification**: Females younger than 18 or older than 45 may have inconsistent menstrual cycles or may be postmenopausal and therefore no longer cycling.
- 2. Must have normal menstrual cycles between 21 and 35 days.
 - **Justification**: Abnormal menstrual cycle lengths or variability in lengths could introduce error variance into the experiment, and could reduce confidence regarding the timing of the experimental manipulation to cycle events.
- **3.** Must be under the **current care** of an outpatient mental health provider, whom they report seeing at CLEAR 2 Study Protocol: Hormones and Suicide Risk, Version 9, 07-02-2020, Page 15 of 64

least once every 3 months.

- Justification: Because we intend to recruit females with current suicidality, engagement with a mental health provider is required as a protective measure to ensure that participants have access to treatment if needed.
- 4. If the woman has children, she must be at least 1 year postpartum.
 - **Justification**: The postpartum period can be characterized by altered hormone levels and changes; therefore, postpartum females may introduce error variance into the experiment.
- 5. Must not be pregnant, breastfeeding, or trying to become pregnant. Pregnancy status will be confirmed using urine pregnancy test at the enrollment visit and again at the first visit of the second condition. Participants will be encouraged to use a barrier method of birth control during the study.
 - **Justification**: Administration of ovarian hormones to a pregnant woman could negatively influence the pregnancy in a variety of ways, including risks to the health of the fetus.
- 6. Must not be taking any form of **exogenous hormones** or IUD, and must have ended previous use of hormonal preparations at least one month prior to the study.
 - **Justification**: The use of additional exogenous hormones poses safety risks and would undermine experimental control of hormones.
- 7. Must be of normal weight (BMI between 18.00-29.99 kg/m2); measured at the enrollment visit.
 - **Justification**: Responses to doses of hormones may vary by BMI and risk for thromboembolic events with hormone use increases in obese females.
- 8. Must report no personal history of any chronic medical condition, including but not limited to metabolic or autoimmune disease, epilepsy, endometriosis, cancer, diabetes, cardiovascular, gastrointestinal, hepatic, renal, or pulmonary disease, and no personal or first degree family history of thromboembolic events.
 - Justification: Administration of exogenous hormones to females with these chronic medical conditions may increase the risk of an adverse health-related response to hormones. Further, the purpose of the present study is to determine the impact of hormonal stabilization (vs. natural withdrawal) in otherwise physically *healthy* females.
- **9.** Must not report 2 or more first degree relatives with hormone dependent cancers (ovarian, uterine, breast, colon, prostate) or a known genetic predisposition (BRCA1, BRCA2, PTEN, or Tp53) to those cancers
 - **Justification**: Administration of exogenous hormones might increase cancer risk in individuals with genetic predisposition.
- **10.** Must not currently smoke **cigarettes**.
 - **Justification**: Administration of ovarian hormones to females who smoke may increase the risk of thromboembolic events.
- **11.** Must not report a history of clinical diagnosis of postpartum depression or premenstrual dysphoric disorder (Note: PMDD diagnosis must have been made based on prospective daily ratings).
 - **Justification**: Some evidence would suggest that the pattern of perimenstrual symptoms that have been linked with these reproductive mood disorders *could* differ meaningfully²⁷ from that which we be expect in the more general clinical population of females with suicidality¹². Because these distinctions are not yet clear, females with a self-reported history of clinical diagnosis with these disorders will be excluded.
- **12.** Must not report any history of manic episode, psychotic symptoms, or substance use disorder.
 - **Justification**: These factors are known sources of variability in suicidality and would therefore introduce error into our models as well as increasing the risk that a participant would experience

CLEAR 2 Study Protocol: Hormones and Suicide Risk, Version 9, 07-02-2020, Page 16 of 64

a suicidal crisis during the study^{17,100}. Use of opioids, methamphetamine, and cocaine will be screened at the enrollment visit to validate self-report measures of substance use.

13. Must report at least some recent suicidal ideation (in the past month) at enrollment.

- Justification: As reviewed in the research strategy, the purpose of the study is to examine the impact of natural perimenstrual hormone withdrawal (vs. prevention of either E2 or P4 withdrawal) on within-person changes in suicide risk. The present sampling strategy **ensures** generalizability²⁴ of our findings to clinical populations of interest and will also prevent a floor effect (i.e., zero-inflation of daily outcome measures and associated limitations in power to detect effects) on primary daily outcome measures (e.g., mediating behavioral constructs, suicidality).
- 14. Must be categorized as having acceptably low imminent risk for suicidal crisis/attempt according to established clinical and research guidelines¹⁰⁰ (see Suicide Experimental Eligibility Table), which have been adapted for the K99/R00 studies (the preceding experiment and the present experiment) in collaboration with [name], the suicide-focused co-mentor on the K99 training grant. As [name] notes in his 2014 methodological paper on research-based suicide risk assessment¹⁸, evaluation of imminent risk of suicidal crisis/attempt is a complex clinical task, requiring integrative consideration of a variety of factors (including: general clinical presentation, ideation severity, frequency, recency, and associated consideration/intent; access to suicidal means; previous attempts and gestures; presence of suicidal planning, recent stressors, frequency of contact with mental health provider; and presence of social support). *Therefore*, our specific criteria for delineating whether a participant is eligible are based on an evidence-based determination^{18,100} that the participant is at acceptably low imminent risk of suicidal crisis/attempt. These decisions will be based on responses to a variety of questions from the SITBI and Severity of Suicidal Ideation Interview (clinical interviews at the beginning of an enrollment visit).
 - Justification: Individuals with current suicidality are not necessarily at imminent risk for suicidal crises/attempt (i.e., their risk is manageable on an outpatient basis through frequent clinical contact, such as the daily calls in the present study). Because the proposed hormone protocol simply prolongs the physiologic luteal hormone profile of E2 or P4, it is not expected to expose participants to additional risk of suicidal crisis beyond what they would naturally experience during their typical monthly menstrual cycles. However, out of an abundance of caution, we will exclude females with elevated imminent risk for suicidal crisis/attempt (determined by structured interview and established guidelines^{18,100}). Individuals with histories of suicidality often have ongoing, habitual thoughts about death or suicide that are highly distinguishable from imminent risk for suicidal ideation at some point in their lives¹¹⁸, yet less than .01% die by suicide each year^{100,118}. Data from the preceding similar experiment (K99 experiment) provide clear evidence of the safety of this protocol; no participant was hospitalized for imminent risk or attempted suicide during the study.

SPECIFICS OF SUICIDE RISK-RELATED ELIGIBILITY CRITERIA

The proposed study will **include** only **participants with current suicidal ideation** (past-month endorsement of suicidal ideation) in order to maximize generalizability to our clinical population of interest. We hypothesize that *natural* perimenstrual withdrawal from ovarian hormones will be associated with significant but transient shifts in continuously-estimated suicide risk that are not expected to escalate to the level of suicidal crisis/attempt (due to the exclusion of certain females at highest risk for attempt, as noted below). In order to minimize the risk of suicidal crises during the study, we will exclude females who meet evidence-based criteria^{18,100} for imminent risk of acute suicidal crisis/attempt.

The goal of these exclusion/inclusion criteria is to **minimize** the risk that a participating woman will demonstrate imminent risk of suicidal crisis/attempt during the study. The determination of acceptably low current risk of suicidal crisis/attempt will be carried out in multiple steps, as follows:

- First, potential participants must pass a phone screen in which they will report on their previous psychiatric diagnoses and recent history of suicide attempts. At that juncture, the following criteria will be applied:
 - a. A woman will be excluded if she reports a suicide attempt or any concrete suicidal planning in the past 3 months, as the majority of repeated attempts occur within the first three months following an initial attempt^{17,100}.
 - b. A woman will be excluded if she reports a history of more than one suicide attempt, as multiple attempts represent a uniquely potent risk factor for additional suicidal crises/attempts^{17,100}.
 - c. A woman will be excluded (and referred) if she reports that she does not currently visit a mental health provider (psychiatrist, therapist) at least once every 3 months¹⁷.
 - d. A woman will be excluded if she reports any extreme external stressors (e.g., death of a loved one, loss of employment) in the past month, as extreme stressors drastically increase the risk of suicidal crisis^{17,100}.
 - e. A woman will be excluded if she reports a history of clinical diagnosis with manic episode, psychotic symptoms, or substance use disorder, as these disorders reduce predictability and increase likelihood of suicidal crises/attempt¹⁰⁰.
- Second, potential participants must pass an in-person eligibility screening at the beginning of an enrollment visit, in which they will complete a clinical interview designed to more thoroughly assess the risk factors described in 1a-1e above, as well as additional determinants of suicide risk outlined in Table 1 below.
 - a. Eligibility criteria in 1a-1e above will again be re-assessed and applied.
 - b. Using a clinical interview based on the SITBI interview¹¹² and the Scale for Suicidal Ideation interview¹¹⁹, the PI will evaluate each woman on a variety of risk factors for suicidal crisis and evaluate whether a woman has acceptably low^{17,18,100} imminent risk of suicidal crisis/attempt using the decision rules described in the leftmost column in Table 1 and summarized below:
 - The evidence-based determination of acceptably low risk^{17,18,100} of suicidal crisis/attempt will be based on the count of positive findings in each Row of Table 1 (see next page), as follows: No positive findings in Row 5; No greater than 1 positive finding in Row 4; No greater than 2 total positive findings in Rows 3 + 4; No greater than 3 total positive findings in Rows 2, 3, and 4.
- 3. Note that ongoing participant suicide risk monitoring and management is described in later sections.

SUICIDE-RELATED EXPERIMENTAL ELIGIBILITY TABLE

The goal of the suicide-related exclusion/inclusion criteria (outlined below) for the proposed set of studies is to **minimize** the risk that a participant will experience an acute suicidal crisis or attempt suicide during the study. Evidence-based criteria were developed in collaboration with mentors at UNC Chapel Hill During the K99 Phase of the Grant^{17,18,100}. History of mania, psychosis, or substance abuse disorder will also be exclusionary. Table notes: Recent = In the past month. MHP = Mental Health Provider. ¹SITBI items 3a, 3b, 4a, 4b, 4c. ²SITBI items 1a, 1b, 1c, 1f, 2c. ³SITBI items 2a, 2b.

	Suicide Attempts ¹		Suicidal Thoughts ²			Recency of Last Suicidal Planning ³	Current Access to Means	Recent Stressors/ Loss	Current Frequency of MHP Contact	Current Social Support	
ROW	Number	Recency	Recency	Recent Frequency	Recent Severity	Recent Intent					
1	Never	Never	In past year	Less than monthly	1f=1	2c=1	Never	No Access to Means	None	>1x/ month	Multiple Strong Supporter s
2 No more than 3 total positive findings allowed in Rows 2,3, +4	Any gesture or NSSI, no attempt	In past 2 years	In past month	~1x/ month	1f=2	2c=2	>2 years ago		Extreme Stressors in past year	~1x/ month	One Strong Supporter or multiple supports
3 No more than 2 total positive findings allowed in Rows 3 + 4	1 aborted attempt	in past year	In past week	~1x/ week	1f=3	2c=3	1-2 years ago	Access to Nonspecific or Unfeasible means	Extreme Stressors in last 3 months	~1/ 2 months	Very Limited Support
4 No more than 1 positive finding allowed in Row 4	1-3 attempts	In past 6 months	Now	>1x/ week	1f=4	2c=4	3 months to 1 year ago	Access to Specific, Feasible Means	Extreme Stressors in last 1-2 months	~1x/ 3 months	No Support
5 No positive findings allowed in Row 5	>3 attempts	In past 3 months					<3 months ago		Extreme Stressors in last month	<1x/ 3 months	

